-Paralysis effecting an area the weighted blanket will cover?

-Current neuromuscular blocking agent

-Presence of recent/unhealed fractures on an area the blanket will cover (e.g., lower limb long bone, rib, pelvis, spine)?

-History of claustrophobia?reported by patient and/or their legally authorized representative (LAR)

-Fever of 37.5C (99.5F) or greater

-Limited English proficiency

LAR Exclusion:

-Not documented in EHR as enrolled participant's LAR

Healthcare Provider Exclusion:

-Not active healthcare provider of enrolled study patient

6. * Will individuals with limited English proficiency be included in or excluded from this research?

- Included
- Excluded - safety concerns if participants are unable to communicate with the study team
- Excluded - instruments/measures only validated in English
- Excluded - no prospect of direct benefit to individual participants
- Excluded - minimal risk study

- Excluded - lack of budget/resources for translation and interpretation [provide an explanation in next question]
- Excluded - other reason [provide an explanation in next question]

7. Justify the inclusion and exclusion criteria if you are either targeting, or excluding, a particular segment of the population / community. Provide a description of the group/organization/community and provide a rationale.

For Patient Participants:

- Excluding those with BMI less than 18.5 due to risk of skin injury from the blankets.
- Excluding those with deficit in cognitive functioning of significant severity that (not expecting to improve) due to inability to identify and track delirium at baseline.
- Excluding those with known pregnancy due to weight of blanket, including abdominal area.
- Excluding prisoners due to vulnerability and inability to consent for study likely requiring LAR consent.
- Excluding those with presence of skin injuries in a location that weighted blanket may add additional pressure because of risk that weight of blanket will increase injury.
- Excluding those with paralysis effecting an area the weighted blanket will cover due to risk of skin injury and autonomic dysreflexia.
- Excluding those with current neuromuscular blocking agent as standard of care is to eliminate any additional risks of skin pressure for these individuals.
- Excluding those with presence of recent/unhealed fractures on an area the blanket will cover (e.g., lower limb long bone, rib, pelvis, spine) due to risk of weight of blanket.

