- Excluding those with a history of claustrophobia reported by patient and/or their legally authorized representative (LAR) due to risk of increased sense of claustrophobia with additional covering on body.
- Excluding those with a fever due to the risk of increasing the fever even greater with placement of the weighted blanket.
- Excluding those with limited English proficiency due to the inability to have translational services directly in Zoom (required when enrolling and engaging with participants at CMH site). May be possible at a later date but the logistics of translation services while using Zoom is beyond the initial abilities of this initial project due to funding limitations.

ID: MS12_HM20027241

View: SF2 - Background, Rationale & Goals Section Complete

Background, Rationale & Goals Section Complete

Protocol Progress:

- ? INITIAL SETUP
- ? **BACKGROUND, RATIONALE & GOALS**
- ? RESEARCH PLAN
- ? CONSENT PLAN
- ? RISKS, PRIVACY & CONFIDENTIALITY
- ? POPULATIONS WITH SPECIAL CONSIDERATIONS
- ? INSTITUTIONAL REQUIREMENTS
- ? DOCUMENTS

Click Continue below to go to the next section

ID: MS12_HM20027241

View: SF2 - Study Procedures

Study Procedures

1. * Describe the study hypothesis and/or research questions. Use lay language whenever possible.

Is the use of weighted blankets feasible and acceptable to prevent and/or mitigate delirium in adult critical care patients in urban and rural settings?

2. * Describe the study's specific aims or goals. Use lay language whenever possible.

Specific Aims

Aim 1: To examine the feasibility and acceptability of weighted blankets as a single component, nonpharmacologic strategy to prevent and/or mitigate delirium in an adult medicine critical care patient population.

Aim 2: To examine the feasibility and acceptability of videoconferencing (VCU Health Zoom), EHR screening, and VCU and VCU Health infrastructure (REDCap, OnCore) for rural participant recruitment and research participation, remote healthcare provider protocol training and research engagement, and remote research monitoring and support for a rural patient population.

Aim 3: To collect preliminary descriptive data and examine trends related the use of weighted blankets to prevent and/or mitigate delirium to inform future efficacy trials in an adult medicine critical care patient population (e.g., agitation, delirium, ICU length of stay, number ventilator days, sedation/opioid medication usage).

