Once informed consent is obtained, medical-grade weighted blankets (equal to approximately 10% of the participants body weight up to 20lbs maximum) will be applied to participants by the bedside nurse for a minimum of 6 continuous hours nightly between 7pm-7am and additional hours as desired by the patient, their LAR, or the patient's clinical care team. Weighted blankets of various weights will be readily available on the nursing unit; the study team will communicate with the bedside nurse regarding what weight blanket will be used for each patient enrolled. Hourly rounding by a study champion will be utilized to document blanket use between the hours of 7pm-7am. Participants will remain enrolled in the study until they are withdrawn (either at participant request, administrative due to an adverse event, or at the request of the clinical team), or they are transferred from an ICU level of care. Data will be collected on: (1) feasibility and acceptability of weighted blankets; (2) feasibility and acceptability of technology to promote rural participation; (3) preliminary descriptive data and trends related to delirium, agitation, ventilator days, length of stay; and (4) participant demographics (see Data Collection Spreadsheet supporting document attached). A REDCap database the incorporates all data points needed to answer study aims will be developed with the assistance from the Wright Center Biostatistical Consulting Laboratory. Data analysis will include descriptive statistics and comparison statistics between VCUMC and CMH. Once the patient's participation ends (withdrawn or transferred from an ICU level of care), the patient (if alert and oriented), the patient's LAR, the patient's nurse, and the patient's physicians and/or advanced practice providers (APPs) will be asked to complete an electronic survey based on their experience with the weighted blanket use. Surveys will only be administered if a patient uses the blanket for at least one night. The survey will be in REDCap; no participant identifiers will be used. The survey will be opened by a member of the study team and brought to the participant on a study dedicated iPad. The study team member will remain in close proximity until the participant indicates they are done. At the time, the study team member will collect the iPad and ensure the survey has been closed. Who the patient's nurse and physicians/APPs are for the day will be determined by the ICU's electronic assignment board and/or care team noted in the EHR via the storyboard.

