Physical risk: The addition of a weighted blanket increases the amount of pressure placed on a patient's skin. Additionally, the weight of the blanket itself increases the risk of injury for the nurse applying the blanket to the patient each night (related to lifting of blanket).

Research data risk: There is a risk of loss of confidentiality and privacy for data collected from the patient's EHR record.

2. * Describe how each of the risks/harms/discomforts identified above will be minimized:

The minimize the physical risk for patients, exclusion criteria have been designed to eliminate enrollment of those with skin breakdown, or risk thereof.

The design of the study includes no additional safeguards for the nurses moving the weighted blankets. However, the weight of the blankets does not exceed lifting requirements of unit nurses. Additionally, proper body mechanics are fundamental to nursing education received by all nurses.

To minimize the risk of loss of confidentiality and privacy, only study team members will have access to the data collected. Additionally, data collected will be stored in REDCap, a secure system endorsed by VCU. Only aggregated, de-identified data will be used for reporting purposes.

3. * Describe any potential risks or harms to a community or a specific population based on study findings (e.g. information that could be stigmatizing or derogatory):

Not applicable.

4. Where appropriate, discuss provisions for ensuring necessary medical, professional, or psychological intervention in the event of adverse events to the subjects:

Although unlikely, any skin injury as a result of weighted blanket use would be medically treated as all other developing skin injuries. Additionally, use of the weighted blanket would immediately cease.

5. * Describe criteria for when the investigator would withdraw an individual participant from the study; such as safety or toxicity concerns, emotional distress, inability to comply with the protocol, etc.:

The investigator would withdrawal an individual participant from the study if any skin changes are noted on daily physical examinations, the patient experiences increased agitation with blanket use as reported by the patient's nurse, or the patient displays a lack of assent over blanket use.

6. * Summarize any pre-specified criteria that would trigger the investigator/sponsor/monitoring committee to stop or change the study protocol due to safety concerns:

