The investigator will re-examine the study protocol if any adverse events occur. Adverse events are based on the risks identified above (patient skin injury or increased agitation, nurse lifting-related injury, loss of participant confidentiality or privacy).

Data and Safety Monitoring

Data and safety monitoring is a system for checking the studys data at regular intervals over the study period to identify and address issues that could affect the safety of research participants. This requirement is in accordance with 45 CFR 46.111.

The purpose of data and safety monitoring plan is to set forth study team procedures for monitoring/addressing:

- Participant safety (physical, psychological, etc.)
- Data validity
- Early stopping (termination) based upon changes in risks and benefits.

7. * Indicate if this study will have a Data Safety Monitoring Board (DSMB) or a Data Safety Monitoring Plan (DSMP): [Required for all greater than minimal risk studies]

- DSMB
- DSMP
- No DSMB/DSMP [Note: This response is not applicable for greater than minimal risk studies]**

ID: MS12_HM20027241

View: SF2 - Privacy

Privacy

Privacy refers to an individual's right to control how others view, record, or obtain information about them. When privacy is violated it can involve such things as

- Being asked personal questions in a public setting;
- Being publicly identified as having a particular characteristic or diagnosis;
- Being seen entering a place that might be stigmatizing;
- Being photographed, videotaped or observed without consent;
- Disclosure of personal information to unauthorized people

Privacy is not the same as confidentiality because privacy protections apply to people, and confidentiality protections apply to data. Confidentiality protections should be described on the Data Confidentiality page of this form, not here.

Instructions for this page:

Select all the applicable ways that the research team will protect participants' privacy throughout the course of the study. **The options listed include some of the most common best practices. Not all will be applicable to every study.**

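### Fever is excluded at entry because the blanket could raise it, but the visible protocol has no rule to withhold the blanket if fever develops after enrolment

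*Combined protocol and SAP*

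**What the plan says.** Study Population, item 5, lists among the patient exclusions "Fever of 37.5C (99.5F) or greater". Item 7 of the same section explains it: "Excluding those with a fever due to the risk of increasing the fever even greater with placement of the weighted blanket".

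Study Procedures, item 6, sets the exposure. The blanket "will be applied to participants by the bedside nurse for a minimum of 6 continuous hours nightly between 7pm-7am", with extra hours if the patient, the representative or the clinical team wants them. Participation lasts until transfer from ICU care or withdrawal, and withdrawal may come "either at participant request, administrative due to an adverse event, or at the request of the clinical team". A study champion rounds hourly overnight to document blanket use.

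The section on Risks, Discomforts, Potential Harms and Monitoring covers what happens on study:

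- Item 1 names one physical risk to the patient: "The addition of a weighted blanket increases the amount of pressure placed on a patient's skin". The other listed risks are nurse lifting injury and loss of confidentiality.
- Item 4 says blanket use stops at once, but only in connection with skin injury.
- Item 5 has the investigator withdraw a participant "if any skin changes are noted on daily physical examinations, the patient experiences increased agitation with blanket use", or if the patient shows a lack of assent.
- Item 6 says: "The investigator will re-examine the study protocol if any adverse events occur". It then says: "Adverse events are based on the risks identified above (patient skin injury or increased agitation, nurse lifting-related injury", and the list ends with loss of confidentiality or privacy.
- Item 7 records that there is neither a monitoring board nor a monitoring plan.

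**The concern.** The fever exclusion rests on what the blanket may do to a febrile patient. That reason does not lapse once the consent form is signed. Participants are enrolled within 72 hours of ICU admission and stay in the study for the rest of their ICU-level care, so a patient who is afebrile at screening can become febrile later. The nightly procedure, read literally, then calls for the blanket in a state that the plan itself treats as unsafe for it.

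Two things are at stake. The first is safety: the protection against a hazard that the plan names depends on unwritten bedside judgement. The second is the Aim 1 feasibility result. If nurses do withhold the blanket for fever without a written rule, they may do so differently at the two sites. Unless the reason is recorded, those nights look the same as nights when the blanket was refused or forgotten. The planned comparison of the two hospitals would then mix safety practice with feasibility.

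**Working it through.** No arithmetic applies: the plan states no figure on this point and none is needed to decide it. The check is to follow two hazards, skin injury and fever, through the same sections.

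| Place in the protocol | Skin injury | Fever |
|---|---|---|
| Entry exclusion, with reason (Study Population, items 5 and 7) | Yes | Yes |
| Listed risk (Risks, item 1) | Yes, as skin pressure | No |
| Instruction to stop using the blanket (Risks, item 4) | Yes | No |
| Withdrawal criterion (Risks, item 5) | Yes, any skin changes | No |
| Named adverse event (Risks, item 6) | Yes | No |

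Skin injury is carried from entry through to adverse events. Fever has the same kind of stated rationale at entry and then drops out. This looks more like an omission than a considered choice.

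Next, the provisions that might cover fever indirectly:

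1. *Daily screening.* In the recruitment text this applies to patients admitted to the two ICUs, as a way to find eligible patients. It does not re-check enrolled participants.
2. *Hourly rounding.* Its stated purpose is to document blanket use. No temperature check is mentioned.
3. *Withdrawal for an adverse event.* Temperature is not among the named adverse events, so this route is not clearly open.
4. *Withdrawal for lack of assent or agitation.* The section on Decisionally Impaired Adults accepts that some patients will be enrolled on the representative's consent alone because illness or sedation prevents alertness. They cannot be relied on to object.
5. *Withdrawal at participant or clinical-team request.* This could cover fever. It is discretionary, has no threshold, and ends participation, whereas a fever may resolve within days.

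After these five, the visible text has no condition that suspends the nightly minimum of 6 continuous hours in a febrile participant, and none that says when use resumes.

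**The case against.** The strongest objection is that key documents are not visible. The device section asks for instructions for use or a description of design, use and risks, and a matching upload is listed as approved. A hold instruction could be there. This stands, and it limits the finding to the visible protocol. A reader might infer that the study has no fever rule anywhere; the documents do not support that.

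A reader might also infer that temperature is not collected, because the HIPAA section's account of health data omits it. That account is a summary. The Secondary Data section refers to the data spreadsheet for the full list of record items. Temperature is presumably charted anyway, since screening from the health record against a 37.5C limit needs it. So it does not follow that the planned trial could learn nothing about this hazard.

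The blanket is placed by an ICU nurse, and the clinical team can have the patient withdrawn. It would go too far to say that febrile patients will in fact be covered. The narrower point remains: the safeguard is unwritten as to fever and has no threshold.

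One might extend the point to neuromuscular blockade started after entry. The exclusion rationale there says that standard of care already removes added skin pressure for these patients, so that case is largely covered and is not part of this finding.

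Finally, Review Setup, item 7, records a continuing-review category in which only data analysis remains. If so, an amendment protects no current participant. This changes the remedy but does not remove the inconsistency.

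**Conclusion.** The point holds for the visible protocol. The nightly rule conflicts with the plan's own reason for excluding fever, and no visible risk, stop-use instruction, withdrawal criterion or named adverse event bridges the gap. The only cover is discretionary withdrawal.

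The size is qualitative. The plan enrols 50 patients, 25 at each hospital. Without an on-study fever rate, neither the number affected nor the number of nights can be estimated, and no harm is shown. The conclusion assumes that the device information, data spreadsheet and consent form contain no hold rule. If one of them does, what remains is to bring that rule into the procedures and risk sections. It should be corrected where blankets are still being applied. Otherwise it matters mainly for how non-use is classified and for the planned randomized trial.

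**What to change.** If blankets are still being applied:

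- In Study Procedures, item 6, with a cross-reference in the withdrawal criteria, state that the bedside nurse checks the latest charted temperature before each nightly application. The blanket is withheld, or removed, while temperature is 37.5C or greater, or at another threshold fixed in advance. It resumes when the fever resolves, without withdrawal from the study.
- Add raised temperature to the listed risks.
- Record a fever hold as the reason for non-use, and report such nights separately from non-adherence in the Aim 1 result, by site.

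A blanket-caused temperature rise should not be added as an adverse event without a defined size, time window and attribution rule. With no control group, ordinary ICU fever could not be told apart from a blanket effect.

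The cost is a short amendment and a look at data already charted, by the nurse who places the blanket. The downside is fewer blanket nights, by an amount that the documents do not allow to be estimated.

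If only data analysis remains, classify non-use nights by reason where records allow, say in the report that no fever rule was in the protocol text, and write the hold rule into the planned randomized trial.
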